# 1 INTRODUCTION

The purpose of this Statistical Analysis Plan (SAP) is to provide a description of the statistical methods to be implemented for the analysis of data from the study with protocol number K-877-ER-201. The SAP will be finalized prior to database lock. Any deviations from the SAP after database lock will be documented in the final Clinical Study Report (CSR).

# 2 STUDY OVERVIEW

# 2.1 Study Objectives

## 2.1.1 Primary Objective

The primary objective of this study is to demonstrate the efficacy of K-877-ER compared to K-877-IR compared to K

#### 2.1.2 Secondary Objectives

The secondary objectives of this study are as follows:

- To demonstrate the efficacy of K-877-ER **Constraints** compared to K-877-IR **Constraints** from baseline to Day 28 in lowering fasting TG levels in patients with fasting TG levels ≥150 mg/dL and <500 mg/dL.
- To evaluate the efficacy of K-877-ER **and** treatments (from **baseline** day to **baseline** to Day 28 in altering pharmacodynamic properties, including lipid parameters, in patients with fasting TG levels ≥150 mg/dL and <500 mg/dL.
- To evaluate the multiple-dose properties of K-877-ER

## 2.2 Study Design

#### 2.2.1 Overview

This is a Phase 2, multicenter, randomized, open-label study investigating the efficacy and profile of K-877-ER treatment (from day to day) compared to K-877-IR treatment (from day) in adult patients with fasting TG levels ≥150 mg/dL and <500 mg/dL. The study consists of a Screening Period, of up to 10 weeks, and a 4-week Treatment Period. During the Treatment Period, patients will receive K-877-ER treatment for K-877-IR treatment Period. During the Treatment Period, patients will receive K-877-ER

Approximately 90 patients (from 12 sites in the United States) who meet all the inclusion criteria and no exclusion criteria will be enrolled in the study. Of the approximately 90 patients enrolled, 24 patients will be enrolled as patients, and will have blood samples for assessments collected.

The Screening Period will occur no more than 70 days and no less than 7 days prior to the first dose of study drug (Day 1, Visit 4). The up to 10-week Screening Period will allow for a 6-week washout period, if needed, followed by up to a 4-week Qualification Period that will be used to assess patient eligibility. At the Screening Visit (Visit 1), a patient's individual TG level must be ≥135 mg/dL and <550 mg/dL.

Patients on non-permitted background lipid-altering therapy must complete a 6-week washout period prior to the first Qualification Period visit (Visit 2). If a patient does not require washout, the patient may start the Qualification Period 24 hours after signing the ICF. Patients may continue through the Qualification Period provided there are no prohibitive safety or eligibility results from the Screening Visit (Visit 1) laboratory tests.

Prior to treatment on Day 1, eligible patients will be randomized in a 1:1:1 ratio to one of three treatment groups. Randomization will be stratified by sex (male or female), statin use (yes or no), and assessment (yes or no).

Treatment Period will occur from Days 1 through 28. On Days 14 and 28, patients will return to the clinical site for efficacy and safety assessments. Patients enrolled as patients will be admitted to the clinical site on Day -1 and confined until discharge on Day 2. On Day 27, patients will be readmitted to the clinical site and confined until discharge on Day 29.

Patients will participate in a Follow-Up Telephone Call 7 days ( $\pm 2$  days) following the last dose of study drug for safety monitoring.

All procedures to be conducted during the study, including timing of all procedures, are described in the Schedule of Procedures.

Selected study procedures will be performed prior to administration of study drug, as applicable.

### Table 1. Schedule of Procedures

		Screening	g Period					
	Screening Visit a,b	Qualification Period c		Treatment Period			Follow-Up	
Visit Name	Visit 1	Visit 2 b	Visit 3 d	Visit 3.1 d,e	Visit 4 d	Visit 5	Visit 6/ET	Telephone Call f
Study Day	-70 to -29	-28 to -21	-21 to -14	-14 to -7	1	14	28	35
Visit Window (days)		±3	±3	±3		±3	±3	±2
Assessment								
Informed consent g	Х							
Inclusion/exclusion criteria	Х	Х	Х	Х	Х			
Fasting TG level		X h	X h	X h				
Serum FSH i	Х							
Pregnancy test j	Х				X k		X k	
Height, body weight, and BMI	Х						X k,l	
Demographic/medical history	Х							
Urine drug screen m	Х							
Prior/concomitant medication	Х	Х	Х	Х	Х	Х	Х	Х
TSH, FT4, and HbA1c	Х							
Randomization					X k			
Physical examination n	Х				X k	X k	X k	
Clinical laboratory tests o	Х				X k	X k	X k	
Vital signs p	Х				Х	Х	Х	
12-lead ECG q	Х				Х		Х	
PD sample r	Х				X k	X k	X k	
Dispense study drug s					Х			
Dosing t					•	— X—		
AEs	•			——————————————————————————————————————				
Study drug compliance check						Х	Х	

a. Patients who are screen failures for a modifiable condition, other than failing the TG criteria, can be re-screened once. Before each patient is re-screened, the Investigator should discuss the case with the Medical Monitor.

b. At the Screening Visit (Visit 1), patients not needing a washout period may start the Qualification Period (Visit 2) 24 hours after signing the informed consent form. Patients may continue through the Qualification Period provided that there are no prohibitive safety or eligibility results from the Screening Visit (Visit 1) laboratory tests.

c. All Qualification Period visits will occur 7 days (±3 days) apart.

d. The last fasting TG Qualification Period visit (Visit 3 or 3.1) should occur ≥7 days prior to Day 1 (Visit 4).

- e. For patients without a qualified medical record, Visit 3.1 is only needed if 1 Qualification Period TG level from Visit 2 or 3 is within 10% of the target range (≥135 mg/dL and <550 mg/dL) and 1 Qualification Period TG level from Visit 2 or 3 is within the target range (≥150 mg/dL and <500 mg/dL).
- f. A Follow-Up Telephone Call will be performed 7 days (±2 days) following the last dose of study drug.
- g. Written consent must be obtained from the patient prior to any study-specific procedure or investigation. including the washout period when applicable.

- i. FSH is to be obtained in women <55 years of age who have not had a menstrual period for ≥1 year. Female patients will be considered postmenopausal if the FSH level is in the central laboratory's normal range for postmenopausal phase.
- j. Female patients of childbearing potential must have a negative serum pregnancy test at the Screening Visit (Visit 1), a negative urine pregnancy test at Visit 4 and Visit 6, and must agree to use effective methods of contraception.
- k. Assessments will be performed prior to dosing.

- 1. Only body weight will be measured at Visit 6 prior to dosing.
- m. A urine drug screen will be performed at the discretion of the Investigator.
- n. At the Screening Visit, a complete physical examination excludes pelvic, rectal, and breast examinations. All other physical examinations throughout the study must include a symptom-directed physical examination, as well as an examination of the heart, lungs, and abdomen and a visual examination of the skin.
- o. Clinical laboratory tests will include hematology, serum chemistry, coagulation, and urinalysis.
- P. Vital signs include systolic and diastolic BP, pulse, respiratory rate, and body temperature and will be measured (sitting) after resting for a minimum of 5 minutes. Patients should avoid smoking, caffeine, or exercise within 30 minutes prior to BP measurement. On Days 1, 14, and 28, BP and pulse must be measured prior to administration of study drug and again approximately 1 hour post-administration.
- q. Patients must be supine for approximately 5 to 10 minutes before ECG collection and remain supine but awake during ECG collection.
- r. PD assessments will be performed under fasting conditions (≥8 hours) and include TG, TC, LDL-C, HDL-C, remnant cholesterol (calculated as TC LDL-C HDL-C), non-HDL-C, FFA.
- s. Study drug, for entire treatment period, will be dispensed to eligible patients on Day 1 (Visit 4), after randomization, via the IRT system.
- t. Daily oral dose will be administered by the patient and taken according to treatment group starting on Day 1 (Visit 4) and concluding on Day 28 (Visit 6) (28 dosing days). Patients in the K-877-IR **Constant** treatment group will receive only the morning dose on Day 28. Study drug will be administered in the fed state at 0 hour with 240 mL of room temperature tap water.

AE = adverse event; **B** = **B** BMI = body mass index; BP = blood pressure; ECG = electrocardiogram; ET = Early Termination; FFA = free fatty acid; FSH = follicle-stimulating hormone; FT4 = free thyroxine; HbA1c = hemoglobin A1c; HBsAG = hepatitis B surface antigen; HCV = hepatitis C virus; HDL-C = highdensity lipoprotein cholesterol; HIV = human immunodeficiency virus; IRT = interactive response technology; LDL-C = low-density lipoprotein cholesterol; PD = pharmacodynamic(s); TC = total cholesterol; TG = triglyceride; TSH = thyroid-stimulating hormone.

# Table 2. Schedule of Procedures (

Visit Name Study Day Visit Window (days)	Scr Screening Visit a,b Visit 1 -70 to -29	reening Qualif Visit 2 b -28 to -21 ±3	Period ication F Visit 3 d -21 to -14 ±3	Period c Visit 3.1 d,e -14 to -7 ±3	Check- In 1 -1	Visit 4 d 1	Discharge 1 2	Treatmo Visit 5 14 ±3	ent Perioc Check- In 2 27	Visit 6/ET 28 ±3	Discharge 2 29	Follow-Up Telephone Call f 35 ±2
Assessment												
Informed consent g	Х											
Inclusion/exclusion												
criteria	Х	Х	Х	Х	Х	Х						
Fasting TG level		X h	X h	X h								
Serum FSH i	Х											
Pregnancy test j	Х				Х				Х			
Height, body												
weight, and BMI	Х									X k		
Demographic/												
medical history	Х											
Urine drug screen I	Х											
Prior/concomitant												
medication	Х	Х	Х	Х	Х	Х	Х	Х	Х	Х	Х	Х
TSH, FT4, and												
HbA1c	X											
Randomization						X m						
Physical												
examination"	X					X'''		X'''		X'''		
Clinical laboratory	N N					Vmn		Vm		Vmp		
	X					Χ ,ρ		X'''		X ,p		
	X					X		X		X		
12-lead ECG4	X					X				X		

#### Table 2. Schedule of Procedures (

(Continued)

Screening Period												
	Screening											
	Visit a,b	Qualif	ication P	Period			Treatment Period				Follow-Up	
		Visit	Visit	Visit	Check-	Visit	Discharge	Visit	Check-	Visit	Discharge	Telephone
Visit Name	Visit 1	2 	3ª	3.1 a,e	In 1	4 ª	1	5	In 2	6/ET	2	Call
		-28										
		to	-21 to	-14								
Study Day	-70 to -29	21	-14	to -7	-1	1	2	14	27	28	29	35
Visit Window												
(days)		±3	±3	±3				±3		±3		±2
Assessment												
PD sample r	Х					Xi		Xm		X m		
Admission to												
clinical site					Х				Х			
Discharge from												
clinical site							Х				Х	
Dispense study												
drug u						Х						
Dosing v						♦		х —		→		
AEs	•					X						
Study drug												
compliance check								Х		Х		

a. Patients who are screen failures for a modifiable condition, other than failing the TG criteria, can be re-screened once. Before each patient is re-screened the Investigator should discuss the case with the Medical Monitor.

At the Screening Visit (Visit 1), patients not needing a washout period may start the Qualification Period 24 hours after signing the informed consent form.
 Patients may continue through the Qualification Period provided that there are no prohibitive safety or eligibility results from the Screening Visit (Visit 1) laboratory tests.

c. All Qualification Period visits will occur 7 days (±3 days) apart.

d. The last fasting TG Qualification Period visit (Visit 3 or 3.1) should occur ≥1 week prior to Day 1 (Visit 4).

e. For patients without a qualified medical record, Visit 3.1 is only needed if 1 Qualification Period TG level from Visit 2 or 3 is within 10% of the target range (≥135 mg/dL and <550 mg/dL) and 1 Qualification Period TG level from Visit 2 or 3 is within the target range (≥150 mg/dL and <500 mg/dL).

f. A Follow-Up Telephone Call will be performed 7 days ( $\pm 2$  days) following the last dose of study drug.

g. Written informed consent must be obtained from the patient prior to any study-specific procedure or investigation, including the washout period when applicable.

- i. FSH is to be obtained in women <55 years of age who have not had a menstrual period for ≥1 year. Female patients will be considered postmenopausal if the FSH level is in the central laboratory's normal range for postmenopausal phase.
- j. Female patients of childbearing potential must have a negative serum pregnancy test at the Screening Visit (Visit 1), a negative urine pregnancy test at Check-Ins 1 and 2, and must agree to use effective methods of contraception.
- k. Only body weight will be measured at Visit 6 prior to dosing.
- 1. A urine drug screen will be performed at the discretion of the Investigator.
- m. Assessments will be performed prior to dosing.
- n. At the Screening Visit, a complete physical examination excludes pelvic, rectal, and breast examinations. All other physical examinations throughout the study must include a symptom-directed physical examination, as well as an examination of the heart, lungs, and abdomen and a visual examination of the skin.
- o. Clinical laboratory tests will include hematology, serum chemistry, coagulation, and urinalysis.
- P. Vital signs include systolic and diastolic BP, pulse, respiratory rate, and body temperature and will be measured (sitting) after resting for a minimum of 5 minutes. Patients should avoid smoking, caffeine, or exercise within 30 minutes prior to BP measurement. On Days 1, 14, and 28, BP and pulse must be measured prior to administration of study drug and again approximately 1 hour post-administration.
- q. Patients must be supine for approximately 5 to 10 minutes before ECG collection and remain supine but awake during ECG collection.
- r. PD assessments will be performed under fasting conditions (≥8 hours) and include TG, TC, LDL-C, HDL-C, remnant cholesterol (calculated as TC LDL-C HDL-C), non-HDL-C, FFA.
- s. On Days 1 (Visit 4) and 28 (Visit 6), patients will remain fasted for at least 4 hours after morning dosing. Patients will not receive any oral fluids other than those used to administer the dose for 1 hour after dosing on Days 1 (Visit 4) and 28 (Visit 6). Study drug will be administered in the fed state at 0 hour with 240 mL of room temperature tap water. patients will remain standing or sitting upright for 4 hours after dosing. except as required by any study procedure.

		l I	
v.	Daily oral dose will be administered by the patient and taken according to treatment group star	ting on Day 1 (Visit 4) and conclud	ng on Day 28 (Visit 6) (28
	desing days) Patients in the K 877 IP treatment group will receive only the mernin	a doco on Doy 28. Study drug will i	he administered in the fed

dosing days). Patients in the K-877-IR teatment group will receive only the morning dose on Day 28. Study drug will be administered in the fed state at 0 hour with 240 mL of room temperature tap water.

AE = adverse event; **EXE** = **EXECUTE** BMI = body mass index; BP = blood pressure; ECG = electrocardiogram; ET = Early Termination; FFA = free fatty acid; FSH = follicle-stimulating hormone; FT4 = free thyroxine; HbA1c = hemoglobin A1c; HBsAG = hepatitis B surface antigen; HCV = hepatitis C virus; HDL-C = highdensity lipoprotein cholesterol; HIV = human immunodeficiency virus; IRT = interactive response technology; LDL-C = low-density lipoprotein cholesterol;

s); PD = pharmacodynamic(s); TC = total cholesterol; TG = triglyceride; TSH = thyroid-stimulating hormone

## 2.2.2 Randomization and Blinding

#### 2.2.2.1 Randomization

On Day 1, prior to dosing, eligible patients will be randomized in a 1:1:1 ratio to 1 of 3 treatment groups. Patients will receive K-877-ER **K**-877-ER **K**-877-ER **K**-877-IR **K** 

Randomization will be stratified by sex (male or female), statin use (yes or no), and

(yes or no). The Investigator or designee will access interactive response technology (IRT) and enter the patient identification number. The IRT system will record the randomized treatment assignment for the patient and assign the appropriate study drug kit.

#### 2.2.2.2 Blinding

This study is open-label.

#### 2.2.3 Study Drug

Study drug, for entire treatment period, will be dispensed to eligible patients beginning on Day 1 (Visit 4), after randomization, via the IRT system.

Patients will receive oral doses of K-877-ER **and and** (one **active** tablet every morning), K-877-ER **active** (two **active** tablets every morning), or K-877-IR **active** (one **active** tablet in the morning and one **active** tablet in the evening) starting on Day 1 and concluding on Day 28 in the fed state. Patients in the K-877-IR **active active** treatment group will receive only the morning dose on Day 28. Study drug will be administered in the fed state at 0 hour with 240 mL of room temperature tap water.

#### Table 3.

K-877-ER	K-877-ER		
K-877-ER	K-877-ER		
K-877-IR	K-877-IR	K-877-IR	

Within 30 minutes prior to study drug administration on Days 1 and 28, patients confined to the clinical site will be administered a meal that is part of a daily diet containing approximately 2300 to 2500 calories, less than 60% carbohydrates, and less than 25% fat. On Days 1 and 28,

patients will remain fasted for at least 4 hours after morning dose. patients will not receive any oral fluids other than those used to administer the dose for 1 hour before and 1 hour after dosing on Days 1 and 28.

patients will remain standing or sitting upright for 4 hours after dosing, except as required by any study procedure. Patients in the K-877-IR **constant** treatment group will receive an evening dose after a meal.

Diet and dosing time should remain consistent for all doses throughout the study. Patients will be instructed by the site to follow dosing instructions on the drug packaging and to return all used, partially used, and unused study drug materials on Day 28.

#### 2.2.4 Sample Size Determination

Approximately 90 patients will be enrolled.

Assuming an effect size delta = 0, pooled SD = 21.38, an alpha = 0.05 (1-sided), and a non-inferiority limit of 15%, a sample size of 26 patients per treatment group provides a power of 0.80.

In the case that the actual effect size delta is 10% (effect of tested regimen 10% less than the reference regimen), the power is then 0.2. If the real effect is different, the result less likely shows non-inferiority.

To account for potential drop off, a total of 90 patients, 30 patients in each treatment group, is planned to be randomized.

# 2.3 Efficacy and Endpoints

#### 2.3.1 Primary Efficacy Endpoint

The primary efficacy endpoint is the percent change in fasting TG from baseline to Day 28. The baseline fasting TG level will be defined based on the protocol version patients consent to. For patients who consented to protocol version 1.0, baseline fasting TG level will be defined as the mean of 3 TG levels: 2 qualification period TG levels within the target range ( $\geq$ 200 mg/dL and <500 mg/dL) and the Day 1 (Visit 4) TG level. For patients who consented to protocol version 2.0, baseline fasting TG level will be defined as the mean of 3 TG levels within the target range ( $\geq$ 150 mg/dL and <500 mg/dL) and the Day 1 (Visit 4) TG level. For patients who consented to protocol version 2.0, baseline fasting TG level will be defined as the mean of 3 TG levels: 2 qualification period TG levels within the target range ( $\geq$ 150 mg/dL and <500 mg/dL) and the Day 1 (Visit 4) TG level for patients who are qualified without a qualified TG medical record. The baseline fasting TG level will be defined as the mean of 2 TG levels: 1 qualification period TG level within the target range ( $\geq$ 150 mg/dL) and the Day 1 (Visit 4) TG level within the target range ( $\geq$ 150 mg/dL) and the Day 1 (Visit 4) TG level within the target range ( $\geq$ 150 mg/dL) and the Day 1 (Visit 4) TG level within the target range ( $\geq$ 150 mg/dL and <500 mg/dL) and the Day 1 (Visit 4) TG level within the target range ( $\geq$ 150 mg/dL and <500 mg/dL) and the Day 1 (Visit 4) TG level for patients who are qualified TG medical record.

#### 2.3.2 Secondary Efficacy Endpoints

The secondary efficacy endpoints include the percent change from baseline to Day 28 for the following:

- Total cholesterol (TC)
- Low-density lipoprotein cholesterol (LDL-C)
- High-density lipoprotein cholesterol (HDL-C)
- Remnant cholesterol (calculated as TC LDL-C HDL-C)
- Non-HDL-C
- Free fatty acids

-	
ļ	
Ī	

# 2.4 Safety Endpoints

Safety assessments include analysis of adverse events (AEs), clinical laboratory evaluations (serum chemistry, hematology, coagulation, and urinalysis), vital signs (blood pressure, pulse rate, respiratory rate, and body temperature), 12-lead electrocardiogram (ECG), and physical examinations.

# **3** STATISTICAL METHODOLOGY

## 3.1 General Considerations

#### 3.1.1 Analysis Day

Analysis day will be calculated from the date of randomization. The day of randomization will be Day 1, and the day immediately before Day 1 will be Day -1. There will be no Day 0.

#### 3.1.2 Analysis Visits

The study consists of a 28-day treatment period where study visits will occur at Visit 4 (Day 1), Visit 5 (Day 14), and Visit 6 (Day 28). Scheduled visits will be assigned to analysis visits as recorded on the case report form (CRF). Unscheduled and early termination visits will be analyzed at the next available visit within the 28-day treatment period. Where multiple measurements for a parameter appear within an analysis visit, the scheduled visit will be used. If there is no scheduled visit and multiple unscheduled visits and/or early termination visits exist within an analysis visit, the later result will be used for the summary measure.

Analysis visits to be assigned are Baseline, Visit 5 (Day 14), and Visit 6 (Day 28).

Any primary or secondary efficacy measurements that have resulted from a non-fasting sample will be considered invalid and will not be used in the derivation of the efficacy endpoint.

### *3.1.3 Definition of Baseline*

For patients who consented to protocol version 1.0, baseline fasting TG level will be defined as the mean of 3 TG levels: 2 qualification period TG levels within the target range ( $\geq$ 200 mg/dL and <500 mg/dL) and the Day 1 (Visit 4) TG level. For patients who consented to protocol version 2.0, baseline for fasting TG will be defined as the mean for 3 TG levels: 2 qualification period TG levels within the target range ( $\geq$ 150 mg/dL and <500 mg/dL) and the Day 1 (Visit 4) TG level for patients who are qualified without a qualified TG medical record. The baseline fasting TG level will be defined as the mean of 2 TG levels: 1 qualification period TG level will be defined as the mean of 2 TG levels: 1 qualification period TG level within the target range ( $\geq$ 150 mg/dL and <500 mg/dL) and the Day 1 (Visit 4) TG level for patients who are qualified TG medical record. The baseline fasting TG level will be defined as the mean of 2 TG levels: 1 qualification period TG level within the target range ( $\geq$ 150 mg/dL and <500 mg/dL) and the Day 1 (Visit 4) TG level for patients who are qualified TG medical record. If any of the TG levels are missing, the average of non-missing TG levels will be used to calculate baseline. Baseline for all other efficacy and safety variables will be defined as the Visit 4 (Day 1) measurement. If the measurement at this visit is missing, the last measurement prior to the first dose of study drug will be used as baseline.

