6.2.2 Qualification Period

During the Qualification Period only samples to measure fasting TG levels will be collected. Patients will fast for a minimum of 8 hours prior to collection of TG samples.

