#### 3.6.3 Vital Signs

Vital signs to be assessed are height, weight, body mass index, temperature, respiratory rate, systolic blood pressure, diastolic blood pressure, and heart rate. Vital signs will be summarized at Baseline, Day 14, and Day 28 using descriptive statistics for the Safety Analysis Set.

At Baseline, Day 14, and Day 28, blood pressure (systolic and diastolic) and heart rate will be taken prior to dosing and one hour after dosing.

Change from baseline at Day 14 and Day 28 will also be summarized. All vital signs measurements will also be listed.

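### The SAP's fallback baseline can use a pre-washout Screening lipid value for the secondary endpoints, and the SAP does not name the baseline blood pressure and pulse reading

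*SAP*

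**What the plan says.** SAP 3.1.3 gives TG its own baseline, an average of Qualification Period and Day 1 values. For everything else: "Baseline for all other efficacy and safety variables will be defined as the Visit 4 (Day 1) measurement". The fallback follows: "If the measurement at this visit is missing, the last measurement prior to the first dose of study drug will be used as baseline".

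Three other provisions decide what the fallback can reach:

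- Protocol 6.2.2: "During the Qualification Period only samples to measure fasting TG levels will be collected".
- SAP 3.1.2, on efficacy values from non-fasting samples: these "will be considered invalid and will not be used in the derivation of the efficacy endpoint".
- SAP 2.2.1: patients on non-permitted lipid therapy complete a 6-week washout before Visit 2. Protocol 4.2 places that washout after informed consent, which is obtained at Visit 1.

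On blood pressure and pulse, SAP Table 1 states: "On Days 1, 14, and 28, BP and pulse must be measured prior to administration of study drug and again approximately 1 hour post-administration". SAP 3.6.3 says of all three analysis visits, baseline included, that "blood pressure (systolic and diastolic) and heart rate will be taken prior to dosing and one hour after dosing", and then calls for change from baseline.

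**The concern.** The secondary endpoints are percent changes in total cholesterol, LDL-C, HDL-C, remnant cholesterol, non-HDL-C and free fatty acids. Their denominator should be the patient's state just before study drug. The fallback carries no condition that the replacement value come from after the washout. If it does not, the recorded change combines the effect of stopping the earlier lipid therapy with the effect of study drug.

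For blood pressure and pulse the issue is a missing definition. SAP 3.1.3 refers to one Visit 4 measurement, but two are scheduled. If the 1-hour reading were taken as the reference, any acute effect of the first dose would be subtracted from the Day 14 and Day 28 changes.

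**Working it through.** **Plan figures.** The plan gives no figure that depends on this rule. Its sample size concerns TG and reproduces: 2 × (21.38 × (1.645 + 0.842) / 15)² = 25.12, so 26 per arm. Power at 26 per arm is 0.80 by the noncentral t distribution. Neither number changes with the baseline rule for other variables.

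**What the fallback reaches for lipids**

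1. The lipid and free fatty acid (PD) sample is scheduled at Visits 1, 4, 5 and 6 (SAP Table 1). Visits 2, 3 and 3.1 collect TG only.
2. If the Visit 4 value is missing, the last scheduled pre-dose value is therefore Visit 1, Day -70 to -29.
3. A non-fasting Visit 4 sample is invalid under SAP 3.1.2. The SAP does not say that invalid counts as missing, but that is the natural reading, and it leads to the same fallback.
4. A washout patient has 42 days between starting washout and Visit 2. With Visit 2 nominally on Day -28 to -21, washout starts no later than Day -70 to -63 (28 + 42 = 70; 21 + 42 = 63). The Visit 1 sample is therefore a pre-washout value.
5. The TG baseline avoids this, because every value it averages is taken at Visit 2 or later.

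**Size for one patient (assumed inputs).** The documents give neither the lipid shift over washout nor its direction. Let the Screening value be (1 + x) times the true Day 1 value, and let p be the true percent change. The recorded change is r = (1 + p)/(1 + x) − 1. The arm-mean shift is k(r − p)/30 for k affected patients among the 30 randomized per arm. With p = 0:

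| x | r | Arm mean, k = 1 | Arm mean, k = 3 |
|---|---|---|---|
| -20% | +25.0% | +0.83 | +2.50 |
| -10% | +11.1% | +0.37 | +1.11 |
| +10% | -9.1% | -0.30 | -0.91 |
| +20% | -16.7% | -0.56 | -1.67 |

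If p is -10%, the individual errors at x = -20% and +20% are +22.5 and -15.0 points. If p is +10%, they are +27.5 and -18.3 points. With 26 patients in the arm, the k = 1 extremes at p = 0 are 25.0/26 = +0.96 and -16.7/26 = -0.64. These are shifts in the raw mean. The mixed model also uses baseline as a covariate, so the shift in its least squares mean will differ somewhat.

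**Blood pressure and pulse.** Only the fallback mentions a pre-dose condition, and it does not apply when a Visit 4 value exists. The rule for multiple values in SAP 3.1.2 is: "Where multiple measurements for a parameter appear within an analysis visit, the scheduled visit will be used". Both readings belong to the scheduled visit, so this rule does not choose between them.

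**The case against.** Using the last pre-dose value is an ordinary convention. The pre-washout case needs two things together: a patient who washed out, and a missing or non-fasting lipid sample at a scheduled on-site visit. For a patient who did not wash out, Screening is only an older value. The documents give no count of washout patients and no rate of missing Day 1 samples, so the size is assumed. All of this stands. It limits the point without answering it, since the value used in such a case is still the wrong reference.

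On blood pressure and pulse, SAP 3.6.3 describes the same pair of readings at each visit, and comparing pre-dose with pre-dose is the natural choice. The fallback's own wording suggests a pre-dose intent, SAP 6 defers detail to separate programming specifications, and all readings are listed. That also stands, so this part is missing detail and no error is shown.

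A reader might infer three stronger things:

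- **That every non-TG variable can take a post-dose baseline.** The schedules mark Day 1 clinical laboratory tests as pre-dose, and SAP Table 1 does the same for the lipid sample. Lipid samples must also be fasting while dosing is in the fed state, and non-fasting efficacy values are invalid. The open question therefore reaches blood pressure and pulse.
- **That the Day 1 ECG is a post-dose reading.** The ECG cell lacks the pre-dose footnote, but that does not show when the ECG is taken. SAP 3.6.4 specifies no ECG change from baseline, although Protocol 9.2.3 does. The documents do not settle the timing.
- **That change from baseline is wrong as planned.** For blood pressure and pulse it is unspecified. For lipids it is wrong only where the two conditions above coincide.

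**Conclusion.** The point holds in a narrow form. The fallback in SAP 3.1.3 can give a washout patient a pre-washout lipid baseline, and nothing elsewhere in the plan prevents it. On the assumed range of -20% to +20%, with a true change of 0%, one affected patient in 30 moves an arm mean by -0.56 to +0.83 points, and three move it by -1.67 to +2.50. More than an occasional case seems unlikely. The effect is confined to the secondary endpoints: TG has its own baseline rule, and the 15% non-inferiority limit is stated for TG only. The documents give no reason to expect the error to favor one arm, but a single case would fall in one arm by chance.

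The blood pressure and pulse baseline needs one clarifying sentence. Every patient has two scheduled Day 1 readings. That shows how widely the definition is needed and is not evidence of a wrong result.

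Both parts are minor. They are worth correcting because the study is open-label and the rule should be fixed before the data are summarized.

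**What to change.** Revise SAP 3.1.3 to state that:

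- baseline for each non-TG variable is the last valid measurement before the first dose of study drug, where valid means fasting for lipids and free fatty acids;
- for blood pressure and pulse, baseline is the pre-dose Day 1 reading, and the 1-hour Day 1 reading is treated as post-dose;
- a non-fasting Day 1 lipid sample counts as missing;
- for patients who washed out lipid therapy, no lipid value from before the washout is used, and if no later pre-dose value exists, baseline is set to missing.

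Align SAP 3.6.3 so that the 1-hour Day 1 reading is no longer labeled as baseline. Body weight is not scheduled at Visit 4, so it keeps its Screening value under this wording.

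The change is to SAP text only. Washout patients can be identified from the medication start and stop dates that Protocol 5.6.4 requires. The cost is an occasional patient lost from a secondary lipid analysis, because percent change cannot be computed without a baseline. The sample size and the primary analysis do not change.
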